STU#: STU00214445

PROTOCOL TITLE: Low Burden Wearable Sensor System for Diagnosing Obstructive Sleep Apnea Over Multiple Nights: Diagnostic Agreement with Home Sleep Testing

PRINCIPAL INVESTIGATOR:

[name] MD PhD
Chief of Sleep Medicine
Northwestern Memorial Hospital
Professor of Neurology
Northwestern University Feinberg School of Medicine
P: [contact]
Email: [contact]
[name]

Sponsor:

National Heart, Lung, and Blood Institute

Sponsoring company:

Sibel Inc
Representative: [name]., MD, PhD.
[name]
[name]
P: [contact]

Confidentiality Statement

The information in this document contains information that is privileged or confidential and may not be disclosed unless such disclosure is required by applicable laws and regulations. In any event, persons to whom the information is disclosed must be informed that the information is privileged or confidential and may not be further disclosed by them. These restrictions on disclosure will apply equally to all future information supplied to you, which is indicated as privileged or confidential.

STU#: STU00214445

Signature Pages

Principal Investigator(s):

Name: [name] MD PhD
Title: Chief of Sleep Medicine
Northwestern Memorial Hospital
Professor of Neurology
Northwestern University Feinberg School of Medicine
P: [contact]
Email: [contact]
[name]

Date:

Sponsor Company:

Name: [name], PhD
Title: Sibel Health's Chief Operating Officer
[name]
[name]
P: [contact]
Email: [contact]

Date:

STU#: STU00214445

PROTOCOL SUMMARY

| | |
|--|--|
| Protocol Title (Long Title) | Low Burden Wearable Sensor System for Diagnosing Obstructive Sleep Apnea |
| Protocol Number | v.1 |
| Study Duration | 4 to 6 months |
| Setting | Northwestern University and Participant’s Homes |
| Sample Size | A total of approximately 100 subjects may be recruited to achieve at least 30 subjects to complete the study (Home Sleep Testing portion). |
| Main Inclusion Criteria | 
 ● Age >22 years old or older ● Subjects with suspected or confirmed OSA based on history ● Persons with a previous diagnosis of OSA ● Subjects with self-reported symptoms of OSA ● Willingness to give consent and comply with study procedures |

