1. LIST OF ABBREVIATIONS

| | |
|---------|--|
| AASM | American Academy of Sleep Medicine |
| AHI | Apnea-Hypopnea Index |
| ECG | Electrocardiogram |
| EDF | European Data Format |
| EDW | Electronic Data Warehouse |
| EHR | Electronic Health Record |
| EMG | Electromyography |
| GCP | Good Clinical Practice |
| HIPAA | Health Insurance Portability and Accountability Act of 1996 |
| HR | Heart Rate |
| HST | Home Sleep Test |
| ICF | Informed Consent Form |
| ICH-GCP | International Conference on Harmonization Good Clinical Practice |
| IRB | Institutional Review Board |
| MRN | Medical Record Number |
| NMH | Northwestern Memorial Hospital |
| NPV | Negative Predictive Value |
| OSA | Obstructive Sleep Apnea |
| ODI | Oxygen Desaturation Index |
| PAP | Positive Airway Pressure |
| PAT | Peripheral Arterial Tonometry |
| PHI | Protected Health Information |
| PI | Principal Investigator |
| PPV | Positive Predictive Value |

STU#: STU00214445

| | |
|-------|--|
| PSG | Polysomnography |
| RPSGT | Registered Polysomnography Technicians |
| RR | Respiratory Rate |
| SDB | Sleep Disordered Breathing |
| SL | Sleep Latency |
| SoC | System-on-Chip |
| TST | Total Sleep Time |

2. OBJECTIVES:

The main objective of this study are as follows:

- Analysis of diagnostic yield from multiple nights with ANNE Sleep
- Analysis of agreement of diagnosis of moderate to severe OSA by determining a patient's Apnea-Hypopnea Index (AHI) wearing the ANNE Sleep system and WatchPAT ONE over one (1) night worn concurrently
- Assessment of usability compared to current HST in the intended population

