4.1 Primary Outcome Measures

- Analysis of variation between nights of AHI derived from ANNE Sleep system across multiple sleep nights at home
- Analysis of agreement for diagnosis of moderate to severe OSA by determining a patient's Apnea-Hypopnea Index (AHI) wearing the ANNE Sleep system and WatchPAT ONE over one (1) night worn concurrently
- Patient responses on psychometric surveys for comfort and usability comparing ANNE Sleep and WatchPAT ONE

•

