The scoring of respiratory events to evaluate for sleep disordered breathing will also follow AASM scoring rules. Apnea-hypopnea index will be used to determine the presence and severity of sleep apnea ($AHI = \text{apneas} + \text{hypopneas} * 60 / \text{TRT}$).

The accuracy (sum of the number of true positives and true negatives divided by the sum of the number of true positives, true negatives, false positives, and false negatives), sensitivity, specificity, positive predictive value, and negative predictive value of the ANNE™ Sleep to detect moderate to severe obstructive sleep apnea will be compared to outputs from WatchPAT ONE. A Bland-Altman plot will be generated with 95% confidence to intervals to assess agreement.

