10. STATISTICAL ANALYSIS

10.1 Sample size

With a sample size of at least 30, the large amount of within-person data provides high statistical power for all planned analyses, allowing this data set to answer all proposed questions while minimizing study costs and any risk to patients.

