10.2 Apnea-hypopnea index (AHI) and oxygen desaturation index (ODI)

1. AHI will be calculated in ranges of 15 – 30 apnea/hypopnea events per hour for moderate OSA and ≥ 30 apnea/hypopnea events per hour for severe OSA. Continuous variables of AHIs during ~~three~~four-night study will be summarized using tables of descriptive statistics. The AHIs with variables will be summarized using counts and percentages. Descriptive statistics will be presented by diagnosis.
2. Diagnostic outcomes will be tabulated and compared for ANNE Sleep vs WatchPAT ONE.
3. Patient preference will be elicited via psychometric surveys for comfort and usability comparing ANNE and WatchPAT ONE.

STU#: STU00214445

4. The oxygen desaturation index (ODI), the hourly average number of desaturation episodes, will also be calculated.

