12. WITHDRAWAL OF PARTICIPANTS

Participants may end their participation at any time during the study. The study investigators may choose to withdraw a study subject if he or she is unable to use the devices or complete the study procedures. The study investigators may withdraw a patient if they develop skin sensitivity or have a medical complication that precludes wearing of the sensors on the suprasternal notch.

If a subject is withdrawn from the study, they will be asked to return the study kit that is given to them at the start of the study. Unless specifically requested in writing, researchers will maintain and use data from patients that end their participation early.

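### Failed or unusable home recordings have no place in the accuracy calculation, no rule in diagnostic yield, and no planned summary by device

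*Combined protocol and SAP*

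**What the plan says.** Section 9.1 computes accuracy as true positives plus true negatives "divided by the sum of the number of true positives, true negatives, false positives, and false negatives". It lists sensitivity, specificity and both predictive values alongside, and these come from the same two-by-two table. Section 10.2 adds that "Diagnostic outcomes will be tabulated and compared for ANNE Sleep vs WatchPAT ONE", without naming a category for no result.

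The first objective in Section 2 is "Analysis of diagnostic yield from multiple nights with ANNE Sleep", but no section gives yield a formula or denominator. The matching primary outcome in Section 4.1 is a different quantity: "Analysis of variation between nights of AHI derived from ANNE Sleep system across multiple sleep nights at home".

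The Protocol Summary sets the target by completers: "A total of approximately 100 subjects may be recruited to achieve at least 30 subjects to complete the study". Under Section 12 the investigators "may choose to withdraw a study subject if he or she is unable to use the devices", and data from those who leave early are kept and used unless the subject asks otherwise in writing.

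No section defines a usable recording, a minimum recording time, a repeat-night rule, an analysis population or the handling of a missing night. The listings in Section 10.3 are adverse events and major protocol deviations. Section 3.3.6 of the appended scoring manual recognises that large movement can invalidate signals, but applies this to single events and not to a whole recording.

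**The concern.** Failure of a home recording is foreseeable. Sections 8.1.3 and 8.1.4 have subjects place the sensors, set up the applications and start the recordings themselves. A night that yields no AHI has not diagnosed anyone, yet the plan gives it no place in agreement, no rule in yield and no summary of its own.

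Two things are at stake. First, the agreement figure describes the devices when they work, and a reader cannot tell how often that was. Second, Night One puts both devices on the same subject on the same night. Whether each produced a usable AHI is therefore an objective, within-subject usability comparison. The survey in Appendix B rates ANNE and has no question that names WatchPAT ONE, so this comparison would add directly to the third objective in Section 2.

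**Working it through.** **Inputs from the documents.** The accuracy formula (Section 9.1); at least 30 completers from about 100 recruits (Protocol Summary); four nights per subject, with both devices on the first (Section 8.1.2).

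**Inputs assumed.** The documents give no failure rate and no expected agreement. I take 30 usable pairs, 27 or 24 of them agreeing, and failure in 5%, 10% or 20% of attempted pairs.

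**1. The plan's own figures.** Neither 30 nor 100 can be reproduced. Section 10.1 says only that "With a sample size of at least 30, the large amount of within-person data provides high statistical power for all planned analyses", with no precision target, effect size or dropout rate. The two figures are linked only by 30/100 = 0.30, an allowance for 70% not to complete.

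**2. Accuracy as defined.** Accuracy = (TP + TN)/(TP + TN + FP + FN). The number of failures does not enter.
- 27/30 = 90.0%, exact (Clopper-Pearson) 95% CI 73.5% to 97.9%.
- 24/30 = 80.0%, exact 95% CI 61.4% to 92.3%.

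**3. Agreement per attempted pair.** Let f be the share of attempted pairs lacking a usable AHI from one or both devices. Attempted pairs = 30/(1 − f), so agreement per attempted pair = (agreeing/30) × (1 − f).

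| f | Attempted pairs | 27 of 30 agree | 24 of 30 agree |
|---|---|---|---|
| 0% | 30.0 | 90.0% | 80.0% |
| 5% | 31.6 | 85.5% | 76.0% |
| 10% | 33.3 | 81.0% | 72.0% |
| 20% | 37.5 | 72.0% | 64.0% |

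The planned report would show the first row in every case.

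**4. Direction of any bias.** Take 30 attempted pairs, 24 usable and 22 agreeing: 22/24 = 91.7%. Had the six failed pairs been classified, agreement would lie between 22/30 = 73.3% (none agree) and 28/30 = 93.3% (all agree). The usable-pair figure sits inside that interval, so missing pairs could move it either way.

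**5. Which device failed.** If all six were ANNE failures, ANNE gave a result in 24/30 = 80.0% of attempts, and 73.3% is the share of attempts ending in an agreeing result. If all six were WatchPAT-only failures, ANNE gave a result in 30/30, and 73.3% says nothing against ANNE. One pooled denominator cannot tell these apart.

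**6. Multi-night completeness.** With independent failure probability p per night, all four nights are usable with probability (1 − p)^4: 81.5%, 65.6% and 41.0% at p = 5%, 10% and 20%. How yield treats an incomplete set of nights therefore matters even at modest failure rates.

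**The case against.** The strongest reply is that the Section 9.1 formula is the standard definition of accuracy. Agreement between two AHIs exists only where both exist, so usable pairs are the right set for that question. This stands: the formula should stay, and the gap is an omission around it.

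Three stronger readings are tempting, and the documents do not support them.

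- **That accuracy and yield are overstated.** Yield has no formula, so nothing shows how a failed night would enter it; it is undefined, not shown to be inflated. Accuracy on usable pairs exceeds agreement per attempt whenever failures occur, but that is a different quantity. Whether it misstates agreement across all recordings depends on whether failure is related to AHI, as step 4 shows.
- **That 100 recruits for 30 completers reveals a device-failure rate.** It is a recruitment ceiling. It can absorb ineligibility, voluntary withdrawal and unfinished nights. Non-completers can also supply valid Night One pairs: Section 11 pays for two nights including Night One, and Section 12 keeps early leavers' data.
- **That device failure will go unreported.** Section 8.2 has a call to confirm that testing succeeded, and Section 10.3 lists major protocol deviations; either may capture some failures. What is missing is a plan to summarise them by device and night.

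It is also fair to object that putting every attempted pair into one agreement denominator would charge a WatchPAT ONE failure to ANNE. That is correct, and the fix has to separate the two.

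**Conclusion.** The point holds as a cheap improvement. Accuracy covers classified pairs only, yield lacks a denominator, and no planned analysis summarises failed or unusable recordings. Results would therefore describe each device on its working nights, and the paired comparison of device success would not be used.

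The size cannot be fixed from the documents. Under the assumed rates of 5% to 20%, a reported 90.0% would stand beside 85.5% to 72.0% per attempted pair. These figures rest on 30 usable pairs, 27 agreeing, and a failure being either device giving no usable AHI. They show how far the two quantities can part; they do not forecast this trial or estimate bias in the planned accuracy.

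**What to change.** Add to Sections 9.1 and 10.2:

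- **(a)** A definition of a usable recording for each device, set before the AHIs are compared. Every item below depends on it.
- **(b)** For all subjects who attempted Night One, including those withdrawn because they could not use a device, a paired usable yes/no table of ANNE by WatchPAT ONE, with each success rate and the paired difference with a 95% CI.
- **(c)** Accuracy on usable pairs kept as the agreement analysis, plus a sensitivity analysis over attempted pairs. This should separate ANNE failure (no index result) from WatchPAT-only failure (comparator missing, not ANNE disagreement) and give best-case and worst-case bounds.
- **(d)** A yield definition in which an attempted night without a usable AHI counts as non-diagnostic.
- **(e)** A flow count from recruited to attempted to usable.

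The cost is some wording and a little more tabulation. Nightly diaries, ANNE uploads, WatchPAT ONE outputs and withdrawal records supply most of the data. No section describes a log of attempted nights, so the completion call may need a field for nights attempted and the reason for any failure. The other downside is a less favourable supplementary figure beside the main one.

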3. INTRODUCTION

Sleep disordered breathing (SDB) is an increasingly common disorder characterized by a pathological increase in upper airway resistance experienced during sleep that ranges from benign snoring to its most severe form of obstructive sleep apnea (OSA). OSA is characterized by recurrent episodes of cessation of breathing and physiological stress as a result of intermittent periods of hypoxemia, and arousals. Studies have demonstrated that OSA leads to profound sleep fragmentation, disturbance of the autonomic nervous system, insulin resistance, increased systemic inflammation, oxidative stress, and subsequent vascular endothelial dysfunction. These physiologic changes cause significant morbidity; OSA is an independent risk factor for wide ranging adverse health outcomes including cardiovascular disease (hypertension, stroke, myocardial infarction), metabolic disorders (insulin insensitivity, diabetes), neurological (dementia), motor vehicle accidents, and mood disorders.¹⁻⁵

The ANNE™ Sleep system has been validated as a diagnostic aid for moderate to severe OSA in a multi-center, open-label clinical study with n=225 subjects. Subjects wore PSG and ANNE Sleep concurrently for one supervised night at a sleep center. Both PSG and ANNE Sleep data were manually scored by 3 blinded registered polysomnography technicians. If AHI values determined by the 3 scorers exhibited great than 15% variation, a board-certified Sleep Medicine physician reviewed the raw data independently per AASM guidelines to account for interscorer variability. The results of the study indicate that ANNE Sleep is sufficiently accurate as an aid to diagnosis of moderate to severe OSA with sensitivity and specificity of 90% and 98% respectively.

4. STUDY ENDPOINTS:

STU#: STU00214445

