6.2 Study Kit Cleaning

Participants will return study supply kits in person by meeting a member of the research team or by mailing them back using pre-paid shipping labels. Study sensors are reusable after completion of study procedures and data collection.

The detailed sanitation instructions for the study kit are attached as **APPENDIX D**.

7. PREPARATION OF WatchPAT ONE

The WatchPAT ONE is a commercialized HST system, which received FDA 510(k) clearance (KK183559). The WatchPAT ONE will be prepared by following its operation manual.

The study coordinator will provide study participants a case with everything needed for a WatchPAT ONE. The case will include:

STU#: STU00214445

- An WatchPAT ONE device. This is a rectangular device that will keep track of body position (information such as whether a person is lying on their back, side, or stomach). It will also store all the information from the system.
- A pulse oximeter. This is a wire with a gray rubber sensor placed on the finger. It will measure pulse, blood flow, and the amount of oxygen in the blood. The pulse oximeter should already be attached to the device.
- A chest sensor. The Chest Sensor monitors snoring, movement, and body position. The chest sensor should already be attached to WatchPAT ONE.
- AA batteries. This will only use these if the batteries inside the HST device stop working.

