9.2 WatchPAT ONE Scoring

The scoring method will be produced in accordance with the device operating manual.

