10.3 Exploratory measurements for research purposes

Additional statistical analyses will be performed to compare outputs of AHI between the different systems. Specifically, these analyses include:

1. Linear regression to establish correlation between AHI determined by ANNE Sleep vs WatchPAT ONE on the same night. Bland-Altman plots will be created to establish bias and 95% confidence intervals of agreement between AHI determined by ANNE Sleep and WatchPAT ONE.
2. Summary statistics of the sensitivity, specificity and accuracy of the classification of the severity of OSA (normal, mild, moderate, and severe OSA) determined by AHI between ANNE Sleep and WatchPAT ONE.
3. Accuracy analysis between AHI determined by ANNE Sleep vs AHI determined by WatchPAT ONE on the same night.
4. Descriptive analysis of patients' characteristics and assessments (e.g. sleep diary) before and after study procedures. Patient characteristics include age, gender, ethnicity, race, height, weight, baseline vital signs, relevant medical and surgical co-morbidities will be abstracted from the medical record or by direct survey of the participants.
5. The listings, specifically adverse events and major protocol deviations, will be ordered by subject.

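### ANNE Sleep's accuracy, sensitivity, specificity and predictive values are computed against WatchPAT ONE, so they measure agreement and should be reported as agreement

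*Combined protocol and SAP*

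**What the plan says.** **The question asked.** The protocol title speaks of diagnostic agreement with home sleep testing. The second primary outcome in Section 4.1 is "Analysis of agreement for diagnosis of moderate to severe OSA", based on one night with both devices worn.

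**The statistics planned.**
- Section 9.1 defines accuracy from counts of true and false positives and negatives. It adds sensitivity, specificity and both predictive values, and says that the ability of ANNE Sleep "to detect moderate to severe obstructive sleep apnea will be compared to outputs from WatchPAT ONE".
- Section 10.3, items 2 and 3, adds "Summary statistics of the sensitivity, specificity and accuracy of the classification of the severity of OSA" and "Accuracy analysis between AHI determined by ANNE Sleep vs AHI determined by WatchPAT ONE on the same night".
- Section 10.2, item 2, plans to tabulate and compare the two devices' diagnostic outcomes, but names no agreement statistic.
- Sections 9.1 and 10.3 plan Bland-Altman plots of AHI. These are the only analyses to which a 95% interval is attached.

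**The comparator.** Section 7 (preparation of WatchPAT ONE) says "The WatchPAT ONE is a commercialized HST system, which received FDA 510(k) clearance". Section 9.2 says only "The scoring method will be produced in accordance with the device operating manual". The documents give no accuracy for WatchPAT ONE.

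**The tests done.** Section 8.1.2 and the schedule of events have both devices on night one and ANNE alone on the other three nights. PSG does not appear.

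**The earlier study.** Section 3 reports "sensitivity and specificity of 90% and 98% respectively" for ANNE in 225 subjects who wore PSG at the same time.

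**The concern.** The terms planned in Section 9.1 describe how well a test finds a disease, and they need a reference standard that settles who has it. In this study the only other test is a second home device. Section 9.1 is loosely worded and might be taken to mean that each device's accuracy will be computed and the two compared. That would need a third test, and none is scheduled. WatchPAT ONE is therefore the only possible source of the true and false labels.

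Two things are at stake. First, Section 3 uses the same terms for the same device and the same target condition, but measured against PSG. Nothing in the plan warns that the new figures are on a different footing. Second, the primary outcome is agreement on a diagnosis, which is categorical. Bland-Altman plots address AHI as a continuous quantity, so the diagnosis itself has only accuracy statistics and a tabulation. It has no named agreement measure, no correction for chance and no interval.

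**Working it through.** **1. The plan's own figure.** There is none to reproduce. No target is set for these statistics. Section 10.1 gives a sample size of at least 30 without a precision goal or a prevalence. The argument does not depend on the sample size.

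**2. Inputs.**
- ANNE against PSG: SeA = 0.90, SpA = 0.98 (Section 3).
- WatchPAT ONE: SeW = SpW = 0.85 to 0.95 (assumed; not in the documents).
- Prevalence p of moderate to severe OSA: 0.3 to 0.7 (assumed; not in the documents).
- Errors of the two devices independent given true status (assumed here, relaxed in step 5).

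**3. Formulas.** With WatchPAT ONE taken as truth:
- apparent sensitivity = [p·SeA·SeW + (1−p)(1−SpA)(1−SpW)] / [p·SeW + (1−p)(1−SpW)]
- apparent specificity = [p(1−SeA)(1−SeW) + (1−p)·SpA·SpW] / [p(1−SeW) + (1−p)·SpW]

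With a perfect comparator these return 0.90 and 0.98.

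**4. Results.** At p = 0.5 and a comparator at 0.85/0.85:
- apparent sensitivity = (0.5×0.90×0.85 + 0.5×0.02×0.15) / 0.5 = 0.384/0.5 = 0.768
- apparent specificity = (0.5×0.10×0.15 + 0.5×0.98×0.85) / 0.5 = 0.424/0.5 = 0.848

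| Assumed WatchPAT Se/Sp | p = 0.3 | p = 0.5 | p = 0.7 |
|---|---|---|---|
| 0.85/0.85 | 64.3% / 91.8% | 76.8% / 84.8% | 83.8% / 72.3% |
| 0.95/0.95 | 80.4% / 96.1% | 85.6% / 93.6% | 88.1% / 88.4% |

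So a device performing exactly as Section 3 reports would show 64–88% and 72–96%. The figures also move with prevalence, although ANNE's accuracy is held fixed.

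**5. Correlated errors.** Keep ANNE at 0.90/0.98 and p = 0.5, and let the two devices' errors overlap as far as they can.
- Comparator 0.85/0.85: (0.5×0.85 + 0.5×0.02)/0.5 = 87%, and (0.5×0.85 + 0.5×0.10)/0.5 = 95%. Both are above the independent-error values but still below 90%/98%.
- Comparator 0.90/0.90: (0.5×0.90 + 0.5×0.02)/0.5 = 92%, and (0.5×0.90 + 0.5×0.10)/0.5 = 100%. Both are 2 points above ANNE's true values. At p = 0.7 the same comparator gives 96.4% and 100%.

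The same true accuracy can therefore appear lower or somewhat higher, depending on quantities that this study does not measure.

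**6. What kappa and intervals would add.** In the worked case of step 4, overall agreement is 0.384 + 0.424 = 0.808. ANNE is positive in 0.5×0.90 + 0.5×0.02 = 0.46 of subjects and WatchPAT ONE in 0.50. Chance agreement is thus 0.46×0.50 + 0.54×0.50 = 0.50, and kappa = (0.808 − 0.50)/(1 − 0.50) = 0.62. On precision, 27 agreements in 30 subjects have an exact 95% interval of about 73–98%, and 14 of 15 have about 68–100%.

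**The case against.** The strongest reply is that this is mostly a matter of words. The title, the objectives and the primary outcome all say agreement. The sentences that introduce the disputed statistics also name WatchPAT ONE as the comparator. The severity-class statistics are placed among the exploratory measures, and no hypothesis or performance goal rests on any of these figures. Positive and negative percent agreement are the same ratios as sensitivity and specificity against WatchPAT ONE, so relabelling changes no number. Section 10.2 already plans the tabulation. All of this stands, and it confines the point to labelling, interpretation and the missing agreement statistics.

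Three stronger inferences are tempting, and the documents do not support them.
- *That the study's conclusion is biased.* The primary outcome is agreement with WatchPAT ONE, and the comparator's errors do not bias an estimate of agreement with that same comparator. They matter only if the figures are read as accuracy for OSA. That readers will do so is a prediction, although the wording of Section 9.1 invites it.
- *That shared errors could carry ANNE to 100%/100%.* Two devices both at 85%/85% with identical errors would show that, but this abandons the 90%/98% of Section 3. With ANNE held there, the results are those of step 5.
- *That shared error is established.* Both devices use a finger probe and a chest sensor. However, ANNE is scored by technicians, its scoring manual lets chest movement alone define an event, and the WatchPAT ONE algorithm is not described. Correlation is possible but undocumented.

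**Conclusion.** The point holds as one of interpretation and reporting. With no PSG and no other reference standard, the Section 9.1 and 10.3 statistics measure agreement with WatchPAT ONE. They do not identify ANNE's diagnostic accuracy, and they are not comparable with the PSG-based figures in Section 3. This follows from the documents alone. The size of the gap does not: the ranges in step 4 rest on assumed WatchPAT ONE accuracy, assumed prevalence and independent errors, and serve only as illustration. The design is not at fault, and the change should be made because it costs almost nothing.

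**What to change.** In Sections 9.1 and 10.3:
- Replace sensitivity, specificity and accuracy with positive, negative and overall percent agreement with WatchPAT ONE at AHI ≥15, each with an exact 95% interval.
- Add Cohen's kappa with a 95% interval.
- Show these beside the cross-tabulation already planned in Section 10.2, item 2.
- Drop PPV and NPV, or label them as conditional agreement (for example, the share of ANNE-positive subjects whom WatchPAT ONE also calls positive).
- State that WatchPAT ONE is a non-reference comparator and that no conclusion about diagnostic accuracy will be drawn from this study.

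The cost is a change of wording, one kappa calculation and a few intervals. No new data, visits or participants are needed. The downside is that the sponsor gives up the terms sensitivity and specificity for this study.
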